5.3 Study Objectives

Primary Safety Objective:

- To assess the safety and tolerability of SARS-CoV-2 Sclamp vaccine compared to placebo.

Primary Immunogenicity Objective:

- To assess the total serum antibody and neutralising antibody (NAb) immune responses elicited by SARS-CoV-2 Sclamp vaccine compared to placebo at Day 29 (28 days after first dose) and Day 57 (28 days after second dose).

Secondary Immunogenicity Objective:

- To compare the total serum antibody and NAb immune responses at Day 1 (baseline), Day 15, Day 29 (28 days after the first dose), Day 43, Day 57 (28 days after the second dose), Day 209 (6 months after the second dose), and Day 394 (12 months after the second dose).

Exploratory Immunogenicity Objectives:

- To follow subjects for 12 months following second study treatment administration to record infections with SARS-CoV-2 and evaluate the frequency and severity of all cases of laboratory confirmed COVID-19 disease.
- To conduct a detailed analysis of humoral and cellular immune responses elicited to Sclamp antigen upon vaccination compared to placebo and comparisons between dosing levels and across time course post-vaccination.
- Assess whether SARS-CoV-2 Sclamp vaccination can cause false positives in subsequent HIV testing. If so, assess duration and range of this response.

5.4 Study Endpoints

Primary Safety Endpoints:

- Frequency, duration, and intensity of solicited local adverse events (AEs), including pain, redness, and induration for 7 days following each study treatment (for Days 1-3, Days 4-7 and Days 1-7).
- Frequency, duration, and intensity of solicited systemic adverse events (AEs), including fever, nausea, chills, diarrhoea, headache, fatigue, and myalgia for 7 days following each study treatment (for Days 1-3, Days 4-7 and Days 1-7).
- Frequency, duration, intensity, duration, and relatedness of unsolicited AEs through to Day 57. Frequency of Serious Adverse Events (SAEs), Medically-Attended Adverse Events (MAAEs), and any AEs leading to study withdrawal (including decision by the Principal

Investigator (PI) not to proceed with the second dose) at any time during study through to Day 394. Frequency and intensity of unsolicited AEs through to Days 57, 209, and 394

Primary Immunogenicity Endpoints:

- Geometric mean titre (GMT) of the serum antibody response to the Sclamp antigen compared to placebo by antigen specific ELISA at Day 29 (28 days after first dose) and Day 57 (28 days after second dose).
- GMT of the serum NAb titres to SARS-CoV-2 virus compared to placebo by MN assay at Day 29 (28 days after first dose) and Day 57 (28 days after second dose).

Secondary Immunogenicity Endpoints:

- Proportion of subjects with ≥ 4 fold increase in titre above baseline by ELISA at Days 15, 29, 43, 57, 209, and 394 post-first study treatment administration compared to placebo.
- Proportion of subjects with ≥ 4 fold increase in titre above baseline by MN assay at Days 15, 29, 43, 57, 209, and 394 post-first study treatment administration compared to placebo.
- GMT of the serum antibody response to the Sclamp antigen compared to placebo by antigen specific ELISA at Days 1, 15, 29 (28 days after first dose), and Days 43, 57 (28 days after second dose) and Days 209 and 394 (6 and 12 months post-second dose respectively).
- GMT of the serum NAb titres to SARS-CoV-2 virus compared to by MN assay at Days 1, 15, 29 (28 days after first dose), and Days 43, 57 (28 days after second dose) and Days 209, 394.

Exploratory Immunogenicity Endpoints:

- Proportion of subjects experiencing laboratory confirmed SARS-CoV-2 infection and/or severity graded COVID-19 disease between Days 57 and 394 compared to placebo.
- Proportion of subjects with titres of $\geq 1:80$ and $\geq 1:160$ by MN assay at Days 1, 15, 29, 43, 57, 209, and 394 compared to placebo.
- Proportion of subjects with ≥ 10 fold increase in titre above baseline by MN assay at Days 1, 15, 29, 43, 57, 209, and 394 compared to placebo.
- Proportion of subjects showing an increase in antigen specific CD4+ T-cells at Days 15, 29, 36, 43, and 57 compared to prevaccination for vaccine antigen dose versus placebo.
- Proportion of subjects showing an increase in antigen specific CD8+ T-cell at Days 15, 29, 36, 43, and 57 compared to prevaccination for vaccine antigen dose versus placebo.
- Evaluation of antibody dependent cellular cytotoxicity (ADCC) at Days 1, 15, 29, 43, 57, 209, and 394 compared to placebo for vaccine antigen dose versus placebo.

- Evaluation of domain specificity of the elicited humoral immune response, specifically the proportion of antibodies elicited to the Receptor Binding Domain (RBD), N-Terminal Domain (NTD), and clamp trimerization domain by a custom Luminex assay and/or ELISA for vaccine antigen dose versus placebo on Days 1, 15, 29, 43, 57, 209, and 394.
- Evaluation of antigen specific humoral immune responses including isotypes IgM, IgA, IgE, and subtypes IgG1, IgG2, IgG3, and IgG4 at Days 1, 15, 29, 43, 57, 209, and 394 compared to placebo by a custom Luminex assay.
- Evaluation of participant blood samples by a range of HIV point of care and rapid diagnostic tests to determine if the post vaccination response results in a false positive outcome, and if so, the rate of false positive detection and duration of the response.

6. Study Design

This will be a single centre, Phase 1, FIH, double-blind, randomised, placebo controlled, single and sequential ascending dose, 4-arm parallel study to evaluate the safety, tolerability, and immunogenicity of the SARS-CoV-2 Sclamp vaccine.

The study will be conducted in two parts: Part 1 will include a young healthy adult population aged ≥ 18 - ≤ 55 years and Part 2 will include an older healthy adult population aged 56 years and over. Part 1 will be a single and multiple ascending dose, 4-arm, parallel study initiated before commencement of Part 2 so that safety can be assessed in the young adult population prior to exposure of the older adult population. Part 2 will be a multiple ascending dose, 3-arm, parallel study.

The study will evaluate a single formulation of SARS-CoV-2 Sclamp protein subunit vaccine administered as a single dose or two doses of varying vaccine antigen concentrations in distinct cohorts.

Four treatments (A, B, C, and D) will be administered to subjects.

This study will consist of 6 cohorts: 2 cohorts of a lower dose (Treatment A), 2 cohorts of an intermediate dose (Treatment B), 1 cohort of a higher dose (Treatment C)(Part 2 only), and 1 cohort of a higher dose, examining both a two dose regimen (Treatment C) and a single dose vaccination regimen (Treatment D) (Part 1 only).

Cohorts 1,2 and 3 will include subjects aged ≥ 18 - ≤ 55 years of age and cohorts 4, 5 and 6 will include subjects aged 56 years and older. Cohorts 4, 5 and 6 will include an approximately equal number of subjects aged ≥ 56 - ≤ 65 years of age, and ≥ 66 years and over.

Part 1: Cohort 1 will include 32 subjects; of these 8 will receive placebo, and 24 subjects will receive Treatment A. Cohort 2 will include 32 subjects; of these 8 will receive placebo, and 24 subjects will receive Treatment B. Cohort 3 will include 56 subjects; of these 8 will receive placebo, 24 subjects will receive Treatment C, and 24 subjects will receive Treatment D.

Part 2: Cohort 4 will include 32 subjects; of these 8 will receive placebo, and 24 subjects will receive Treatment A. Cohort 5 will include 32 subjects; of these 8 will receive placebo, and

24 subjects will receive Treatment B. Cohort 6 will include 32 subjects; of these 8 will receive placebo, and 24 subjects will receive Treatment C.

Treatment	Dose regimen
Treatment A (Cohorts 1 & 4)	SARS-CoV-2 Sclamp vaccine 1 x 5 mcg, or placebo, administered in a two dose regimen, at least 28 days apart
Treatment B (Cohorts 2 & 5)	SARS-CoV-2 Sclamp vaccine 1 x 15 mcg, or placebo, administered in a two dose regimen, at least 28 days apart
Treatment C (Cohorts 3 & 6)	SARS-CoV-2 Sclamp vaccine 1 x 45 mcg, or placebo, administered in a two dose regiment, at least 28 days apart
Treatment D (Cohort 3 only)	SARS-CoV-2 Sclamp vaccine 1 x 45 mcg, or placebo, administered as a single dose, followed by placebo as the second dose at least 28 days apart

Sentinels will be used for cohorts 1, 2 and 3 such that the first two subjects will receive either the first dose of SARS-CoV-2 Sclamp vaccine or placebo. After at least 24 hours from the time of administration of the first doses a review of the immediate post-vaccination safety data will be conducted by the Safety Review Committee (SRC) in accordance with the study protocol. Should there be no safety concerns, the remaining subjects in each cohort will be dosed. The step-wise dose escalation study design is an additional precautionary measure, where the lower dose cohort will complete their first vaccination, and the cumulative safety data from the first 7 days will be evaluated by the SRC prior to initiating vaccination with the next higher dose of vaccine.

[figure not shown]
Despite consisting of 2 separate treatments, Cohort 3 will include only include 2 sentinels, 1 placebo and 1 active from Treatment C only, as Treatments C and D are functionally identical until the second dose of active or placebo (respectively) is scheduled 28 days later. The sentinel will not be randomised between Treatment C and D as Treatment D will receive placebo as a second dose, and accordingly no sentinel is required to ensure optimal safety.

Cohorts will be dosed sequentially, and escalation from Cohort 1 to Cohort 3 will be authorised by the SRC if no safety events of concern are observed in subjects up to Day 8 following review of the cumulative safety data of each Cohort.

After the first vaccination dose has been administered to Cohorts 1, 2 and 3 and the aggregated safety data reviewed by the SRC, vaccination will be initiated for Cohorts 4, 5 and 6. These Cohorts will not include sentinels, however, the SRC will review the aggregated/cumulative safety and tolerability data up to at least Day 8 post vaccination for all subjects in each of Cohorts 4, 5 and 6 by cohort before proceeding to the second vaccination dose.

The same authorisation review process will again be repeated at the second dose.

The study design is summarised in Figure 1.

¹ As Treatments C and D are functionally identical until Day 29, the active sentinel subject from Treatment C will serve as a sentinel for both treatments at first dose. At second dose, no sentinel is required for Treatment D as the placebo will be administered.

Figure 1: Visual Schematic for Study Design**6.1 Study Progression and Evaluations**

The study will progress from Cohort 1 to Cohort 2, and from Cohort 2 to Cohort 3 when the cumulative safety data of the previous cohort up to Day 8 have been collected and, reviewed by the SRC, and who will provide authorisation to proceed to the next dose cohort by the process described in Section 7.1. Vaccination for Cohorts 4, 5 and 6 will be initiated only once the SRC have completed their review of the aggregated safety and tolerability data from Cohorts 1, 2 and 3.

Adjustment to the currently outlined subsequent dose level, dosing regimen, and period of subjects' follow-up may be made by the SRC based on data from the prior completed dose level. However, the total dose to be administered in a given cohort will not exceed the one currently outlined in the protocol.

6.2 Starting Dose

The planned starting dose of 5 mcg administered twice in subjects has been selected based on reported dose levels of comparable viral subunit vaccines approved for use (as described in Section 5.2.2, and the IB). Of these comparable vaccines highlighted, the selected dose represents between a 3- to 18-fold decrease (compared to RECOMBIVAX HB[®] and GARDASIL[®]9 respectively) in total exposure, therefore this initial starting dose is deemed to be a suitable dose to establish initial safety information for the SARS-CoV-2 Sclamp vaccine for dose escalation purposes.

6.3 Dose Escalation Scheme

7. The proposed escalation scheme for the study consists of two three-fold dose increments. The planned dose range of 5 mcg to 15 mcg to 45 mcg administered twice 28 days apart was selected to minimize the risk to the subjects while ensuring the evaluation of an exposure range that encompasses and exceeds the expected level to achieve an immunological response. Dose Escalation Criteria

7.1 Data Review by the Safety Review Committee

The SRC will be responsible for the assessment of available safety and tolerability data for each cohort and to make decisions with regards to study progression through the three cohorts in Part 1 and prior to initiating vaccination for Part 2. The SRC will be composed of at least the PI, one Sponsor representative, and a Syneos Health Medical Monitor. Additional non-voting members of the SRC may also be included in the SRC to contribute to discussions, but will not have a vote in the decision to progress to a new cohort. The conduct of the SRC during the study will be as dictated in the SRC Charter.

In Part 1, for the purpose of progressing from sentinels to dosing the rest of cohort (ROC), an informal SRC discussion will be held after the sentinel's safety data are available for 48-hours post dose (Day 2). If no AEs of note, SAEs, or severe AEs, dosing of the ROC may be conducted

without a formal SRC meeting, and dosing may commence with email confirmation from the SRC members (this process will be repeated again following administration of the second dose).

For the purpose of progressing from Cohort 1 to Cohort 2 and from Cohort 2 to Cohort 3, a formal SRC meeting will be held after aggregated safety and tolerability data up to at least Day 8 (7 days post-first dose) are available for all eligible subjects from each cohort before proceeding with vaccination of the next cohort (and similarly up to at least Day 36 following the second vaccination dose at Day 29). As the maximal immunological response is not expected to be reached by Day 8, immunological data will not be assessed as part of the SRC decision making process.

The potential decisions of the SRC are:

1. Escalate to the next planned dose level; or
2. Suspend dose escalation until further review of study data can be made, allowing the SRC to determine whether predefined halting rules have been met. Dose escalation may resume once the SRC concludes that no halting rules have been met; or
3. Stop dose escalation;
4. Terminate the study.

The SRC will conduct a blinded review of the data; however the blind may be broken for individual subjects if judged necessary, prior to making a decision on dose escalation. Dose escalation may occur only following mutual agreement between the SRC members. Decisions taken by the SRC will be documented and submitted to the HREC overseeing the study, along with supportive data.

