	
dose of SARS-CoV-2 Sclamp vaccine administered in a two dose regimen 28 days apart).
 
A total of 216 subjects are planned to be included in the study.
 
Since this is a FIH study with a novel vaccine antigen, a conservative approach to vaccine dosing will be adopted to ensure safety of study subjects. Sentinels will be used for each of cohorts 1, 2 and 3 such that two randomly selected subjects will receive either the first dose of SARS-CoV-2 Sclamp vaccine or placebo on Day 1 (and again on Day 29 for the second dose). After at least 24 hours from the time of administration of the first dose a review of the immediate post-vaccination safety data will be conducted by the Safety Review Committee (SRC) in accordance with the study protocol. Should there be no safety concerns the remaining subjects in the cohort will be dosed. The step-wise dose escalation study design is an additional precautionary measure, where the lower dose cohort will complete their first vaccination, and the cumulative safety data from the first 7 days will be evaluated by the SRC prior to initiating vaccination with sentinels of the intermediate dose of vaccine; same repeated at next (higher) dose level. After the first vaccination dose has been administered to Cohorts 1, 2 and 3 and the aggregated safety data reviewed, vaccination will be initiated for Cohorts 4, 5 and 6.
 
Subjects will also have access to an electronic diary to capture solicited and unsolicited AEs and a memory prompt for symptoms of COVID-19. A paper diary will be available for those subjects in Cohorts 4, 5 and 6 who do not have a device that can support the eDiary application. Subjects will be instructed to advise the clinical site if they have been diagnosed with COVID-19, shown symptoms of COVID-19, or returned from overseas in the interim period. Where an acute respiratory illness, or any other relevant signs or symptoms that are clinically suspect for COVID-19, is identified and confirmed by nasal/oropharyngeal swab and SARS-CoV-2 specific polymerase chain reaction (PCR), subjects will be advised to contact the clinical site immediately. Subjects will be given an information sheet that defines the symptoms for COVID-19 at the time of receipt of their first study vaccination.

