Safety Review Committee	
A Safety Review Committee (SRC) will be implemented to review safety data during scheduled periodic reviews. For Part 1 Cohorts 1, 2 and 3 the SRC will review safety data as described in the SRC charter and in the statistical analysis plan after safety data is available up to 48 hrs after dosing of the first 2 sentinel subjects in each cohort before proceeding with vaccination of the remaining subjects in each cohort (this process will be repeated again following administration of the second dose). In addition, the SRC will review the aggregated/cumulative safety and tolerability data up to at least Day 8 for all subjects in each cohort before proceeding with vaccination of the next cohort (and similarly up to at least Day 36 following the second vaccination dose at Day 29).
 
Once all subjects in Part 1 have completed their first vaccination and safety evaluation, dosing will commence for Part 2 subjects (Cohorts 4,5 and 6). The SRC will review the aggregated/cumulative safety and tolerability data up to at least Day 8 for all subjects in Cohorts, 4, 5 and 6 before proceeding to the second vaccination dose.
 
Pausing rules are defined in the protocol.

Expected Start and End Dates:	
The clinical portion of the study should last approximately 14 months, consisting of approximately 2 months in the active study portion and a further 12 months of follow-up. Cohort 1 is expected to start in July 2020, and Cohort 6 is expected to complete the active study portion (up to Day 57) in December 2020, with the 12 month post-second dose assessments expected to be completed for Cohort 6 in November 2021.

3. List of Abbreviations and Definition of Terms

ADCC	Antibody Dependent Cellular Cytotoxicity
AE	Adverse Event
AESI	Adverse Event of Special Interest
ALP	Alkaline Phosphatase
ALT	Alanine Aminotransferase
ASC	Antibody Secreting Cell
AST	Aspartate Aminotransferase
BP	Blood Pressure
BUN	Blood Urea Nitrogen
CFR	Code of Federal Regulations
CK	Creatinine Kinase
COPD	Chronic Obstructive Pulmonary Disease
COVID-19	Coronavirus Disease 2019
CRF	Case Report Form
CSR	Clinical Study Report
CV	Coefficient of Variation
ECG	Electrocardiogram
eCRF	Electronic Case Report Form
EDC	Electronic Data Capture
ELISA	Enzyme-Linked Immunosorbent Assay
EMA	European Medicines Agency
FDA	Food and Drug Administration
FIH	First In Human
FSH	Follicle Stimulating Hormone
GCP	Good Clinical Practice
GGT	Gamma-glutamyltransferase

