5.2 Rationale for Study Design

This will be a single centre, Phase 1, FIH, randomised, double-blind, placebo controlled, single and multiple ascending dose, 4-arm, parallel study.

The study will be conducted in two parts: Part 1 will include a young healthy adult population aged ≥ 18 - ≤ 55 years and Part 2 will include an older healthy adult population aged 56 years and over. Part 1 will be a single and multiple ascending dose, 4-arm, parallel study initiated before commencement of Part 2 so that safety can be assessed in the young adult population prior to exposure of the older adult population. Part 2 will be a multiple ascending dose, 3-arm, parallel study.

Since this is a FIH study with a novel vaccine antigen, a conservative approach to vaccine dosing will be adopted to ensure safety of study subjects. Sentinels will be used for cohorts 1, 2 and 3 such that two randomly selected subjects will receive either the first dose of SARS-CoV-2 Sclamp vaccine or placebo on Day 1 (and again on Day 29 for the second dose). After at least 24 hours from the time of administration of the first doses a review of the immediate post-vaccination safety data will be conducted by the Safety Review Committee (SRC) in accordance with the study

protocol. Should there be no safety concerns, the remaining subjects in the cohort will be dosed. The step-wise dose escalation study design is an additional precautionary measure, where the lower dose cohort will complete their first vaccination, and the cumulative safety data from the first 7 days will be evaluated by the SRC prior to initiating vaccination with sentinels of the intermediate dose of vaccine; same repeated at next (higher) dose level. After the first vaccination dose has been administered to Cohorts 1, 2 and 3 and the aggregated safety data reviewed, vaccination will be initiated for Cohorts 4, 5 and 6.

Subjects will be randomised into 1 of 4 treatment arms across 3 cohorts in Part 1 or into 1 of 3 treatment arms across 3 cohorts in Part 2, in a double-blinded manner. The double-blind will be maintained from first randomisation of an eligible subject until, at least, collection of data for all subjects is complete up to Day 57. After this day, the treatment assignment will be unblinded for all study team members, however subjects will remain blinded for the duration of the study.

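### Part 1 first-dose sentinel hold: three places in the protocol allow release after at least 24 hours, two require 48 hours of data, and Section 7.1 labels 48 hours as Day 2

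*Protocol*

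**What the plan says.** Five places in the protocol describe the hold between the first-dose sentinels and the rest of each Part 1 cohort.

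Three set a 24-hour floor, after which the remaining subjects are dosed if there is no safety concern:

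- Synopsis, Study Design: "After at least 24 hours from the time of administration of the first dose a review of the immediate post-vaccination safety data"
- Section 5.2: "After at least 24 hours from the time of administration of the first doses"
- Section 6: "After at least 24 hours from the time of administration of the first doses a review of the immediate post-vaccination safety data"

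Two require 48 hours of data:

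- Synopsis, Safety Review Committee: data "up to 48 hrs after dosing of the first 2 sentinel subjects in each cohort before proceeding with vaccination of the remaining subjects"
- Section 7.1: "safety data are available for 48-hours post dose (Day 2"

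For the second dose, the synopsis SRC row repeats its own 48-hour procedure ("this process will be repeated again following administration of the second dose"), and Section 7.1 does the same. Section 6 says only "The same authorisation review process will again be repeated at the second dose", with no interval.

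The day count can be read from Section 7.1 itself, where the gate between cohorts uses "aggregated safety and tolerability data up to at least Day 8 (7 days post-first dose". The synopsis Clinical Visits row, footnote 4 of the Schedule of Events and Section 9.10.1 all treat Day 2 as the 24-hour assessment.

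**The concern.** The sentinel hold is the first gate at each dose level in a first-in-human trial of a novel antigen. A minimum hold exists to say when release is first allowed, and here the protocol gives two answers. A team working from the study design sections could release at 24 hours and breach the SRC sections.

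The Day 2 label makes this worse, because Day 2 is the 24-hour clinic visit. Section 7.1 therefore gives 48 hours in words and the 24-hour visit by label. It also lets the rest of the cohort be dosed on email confirmation, without a formal meeting, if nothing of note has occurred, so the written timing carries weight. With two minimums on paper, it cannot be said whether a release between them was a protocol deviation.

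**Working it through.** **Two minimums.** Let *r* be the hours from the sentinel dose to release of the remaining subjects.

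| Place | Condition | *r* from 24 to under 48 | *r* of 48 or more |
|---|---|---|---|
| Synopsis, Study Design | *r* ≥ 24 | met | met |
| Section 5.2 | *r* ≥ 24 | met | met |
| Section 6 | *r* ≥ 24 | met | met |
| Synopsis, SRC | *r* ≥ 48 | breached | met |
| Section 7.1 | *r* ≥ 48 | breached | met |

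Below 48 hours the score is three met and two breached. Of the two stated intervals, only 48 hours meets all five. The gap is 48 − 24 = 24 hours.

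**The day label.** Dosing is on Day 1, so study day = 1 + hours post-dose / 24.

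- Check against the protocol: 7 days gives 1 + 7 = Day 8, and 28 days gives 1 + 28 = Day 29, both as stated.
- 24 hours: 1 + 24/24 = Day 2.
- 48 hours: 1 + 48/24 = Day 3, not Day 2.
- After a Day 29 dose, 48 hours: 29 + 48/24 = Day 31.

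The time of dosing does not rescue the label. With calendar days and a dose given *t* hours after midnight on Day 1 (0 < *t* < 24), Day 2 runs from 24 − *t* to 48 − *t* hours post-dose, so it always ends before 48 hours. With an assumed 09:00 dose, Day 2 covers 15 to 39 hours. Numbering the dose day as Day 0 would make 48 hours Day 2, but it contradicts dosing on Day 1 and the Day 8 and Day 29 equivalences above.

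**Subjects behind the gate.** Each Part 1 cohort has two sentinels and one first-dose gate, so there are three gates. Non-sentinels number 32 − 2 = 30, 32 − 2 = 30 and 56 − 2 = 54, a total of 114 of 120 (95%). This includes placebo recipients.

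**Second dose.** The 24-hour sentences name the first dose, and the two 48-hour places are the ones that expressly repeat their process. Only the general sentence in Section 6 could carry 24 hours forward, and it gives no interval. No express second-dose conflict follows beyond the shared Day 2 label.

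**The case against.** The best defence is that the texts can be reconciled. At least 24 hours is a floor, the three places that use it are design overviews, and Section 7.1 is the operative SRC section. A team that waits 48 hours breaches nothing, release needs SRC confirmation in any case, and the SRC Charter, which is not at hand, may fix the interval. It is true that 48 hours satisfies everything and that the Charter may govern practice. But a 24-hour floor still permits a release that the SRC sections forbid, and a charter does not correct the protocol text.

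Second, timing. Version 2.2 is dated 2 November 2020, Cohort 1 was expected to start in July 2020, and Cohort 6 was expected to finish Day 57 in December 2020. Day 57 is 56 days after Day 1, which puts Cohort 6 first doses between about 6 October and 5 November. Part 2 follows review of the Part 1 first doses, so the three gates had probably passed by about the time of this version. These are expected dates, not actual ones. The point lowers urgency; one rule is still needed to judge whether any release was a deviation, and the label also applies to the second-dose review.

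Third, the protocol does not define study days as midnight to midnight. Counted in 24-hour blocks from dosing, Day 2 runs from 24 to 48 hours. Even so, the 48-hour point is where Day 3 starts, and footnote 4, which allows the assessment at any time on Day 2, fits calendar days better.

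Fourth, 24 hours may have been the intention: three of the five statements, the label, and the absence of a visit between Day 2 and Day 8 are all compatible with it. That is fair. The defect itself requires only one interval used throughout; 48 hours is recommended because it is the conservative choice and the only stated interval that meets all five statements.

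**Conclusion.** The concern holds. For the Part 1 first-dose sentinel hold, the protocol fixes two minimums that differ by 24 hours, at three gates standing before 114 of 120 subjects, and Section 7.1 gives the wrong study day for 48 hours. It is an inconsistency in a safety rule and should be fixed.

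Its reach is limited. SRC confirmation, the halting rules and the Day 8 gate between cohorts apply under either reading, and no endpoint, analysis population or analysis changes. The contradiction is read directly from the text; the day label rests on the protocol's own day numbering. Whether any cohort was actually released before 48 hours cannot be known from the protocol.

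**What to change.** - In the synopsis Study Design row, Section 5.2 and Section 6, change the 24-hour floor to at least 48 hours.
- In Section 7.1, change the label to Day 3 (Day 31 for the second dose).
- Add one sentence saying that the SRC reviews the sentinels' Day 2 or Day 30 clinic data together with their diary entries through 48 hours.

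This is wording in four places plus one sentence. The hold lengthens by up to one day per first-dose gate, so up to 3 × 24 = 72 hours (three days) over the sequential cohorts, and by nothing for gates already passed.

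The 48-hour diary check is a newly specified step: no visit is scheduled between Day 2 and Day 8, and Section 9.15.2 ties diary review and interview to study visits. It needs no new visit, because Schedule of Events footnote 13 already has symptom entries made daily on Days 1 to 8 and 29 to 36, and footnote 12 already provides for diary review for safety oversight.
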